## **9.2 Secondary, Other and Subgroup Efficacy Endpoint Analyses**

### **9.2.1 Secondary Efficacy Endpoint Analyses**

The mean IOP values will be analyzed similarly as the mean IOP change from baseline as described in section 9.1. That is, summary statistics (N, mean, SD, min and max) of IOP values at each scheduled hour of each visit. Also, analyses of IOP values will be performed using an ANCOVA model with treatment as main effect and hour-matched baseline IOP as covariate

### **9.2.2 Other Efficacy Analyses**

For each visit at Baseline, Day 4 and Day 14, a mean diurnal IOP value will be calculated for each subject by taking the average of the IOP value at all hours (0, 2, 4, and 8). The change from baseline mean diurnal IOP value will be analyzed by the ANCOVA model similarly as the primary efficacy endpoint analysis (section 9.1). In addition, the mean diurnal IOP value will be analyzed by the ANCOVA model similarly as the secondary efficacy endpoint analysis (section 9.2.1).

## **9.3 IOP Analysis of Non-Study Eye**

Summary statistics of IOP values of non-study eyes will be provided by Day and Hour for each treatment group. Efficacy analysis (sections 9.1, 9.2.1 and 9.2.2) will also be carried out for non-study eye.

## **9.4 Interim Analysis**

No interim statistical analysis is planned.

## **10 SAFETY ANALYSIS**

Listings will be presented for all of the safety parameters (section 5.4) for Part 1 and 2 of the study, with the exception of adverse events, which will be summarized as described below. For slit-lamp biomicroscope and visual acuity parameters, potentially clinically significant findings will be flagged according to pre-defined criteria in the listings.

### **10.1 Safety Endpoint Analysis**

#### **10.1.1 Adverse Events**

All adverse events (AEs) reported during the study will be recorded and coded using MedDRA version 20.1 terminology. An AE will be considered as treatment-emergent if it has an onset during the treatment period or is pre-existing and worsens after the first dose of study medication is administered. Subjects may have more than one AE per System Organ Class (SOC) and Preferred Term (PT). At each level of subject summarization, a subject will be counted once if they reported one or more events and will be reported with the highest severity. In cases where severity or relationship is missing, the most conservative approach will be taken (i.e., highest severity and assumed to be related).

For Part 2 of the study, the number, and percent of subjects with adverse events will be tabulated by PT using counts and percentages by treatment groups. This summary will include all treatment emergent adverse events (TEAEs) regardless of causality, treatment-related TEAEs, all serious AEs, treatment-related serious AEs, and all adverse events leading to premature discontinuation of study treatment. A separate summary will also be produced for TEAEs by SOC and PT. For Part 1 of the study, no summary presentation of adverse events will be carried out.

Both parts of the study will present a listing of TEAEs by SOC and PT showing adverse events location (OD, OS or non-ocular), severity, relationship, discontinuation details, and action taken. Also, listing for serious adverse events, and adverse events leading to discontinuation will be generated for both parts of the study.

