### **8.7.1. Procedures for Collecting and Reporting Adverse Events**

Adverse events will be assessed, documented, and recorded in the eCRF throughout the study (ie, after informed consent has been obtained). At each visit, the investigator will begin by querying for adverse events by asking each subject a general, non-directed question such as “How have you been feeling since the last visit?” Directed questioning and examination will then be done as appropriate. All reported adverse events will be documented on the appropriate eCRF.

If, after obtaining the subject’s informed consent but prior to administration of study product/treatment, a medical condition is identified via a study entry protocol assessment or procedure (eg, screening ECG test) which, based on the Investigator’s judgment (and in consultation with the subject), is determined to be a pre-existing condition (ie, a condition existing prior to the time of the subject’s informed consent), it should be documented on the

appropriate eCRF. Otherwise, the condition should be reported as a pre-treatment adverse event.

All adverse events that are drug-related and unexpected (not listed as treatment-related in the current Investigator's Brochure) must be reported to the governing Institutional Review Board/Independent Ethics Committee (IRB/IEC) as required by the IRB/IEC, local regulations, and the governing health authorities.

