### **9.3.2. Safety Analyses**

All safety analyses will be performed on the Safety Population.

The Medical Dictionary for Regulatory Activities (MedDRA) nomenclature will be used to code adverse events. A detailed definition of treatment emergent adverse events (TEAEs) will be provided in the SAP. The number and percent of subjects with adverse event reports will be tabulated for all treatment emergent adverse events (TEAEs) regardless of causality, treatment-related TEAEs, all serious TEAEs, treatment-related serious TEAEs, and all adverse events leading to premature discontinuation of study treatment.

For Part 2, analyses of macroscopic hyperemia and hyperemia as evaluated on biomicroscopy will include evaluation of peak severity at each post-baseline visit (Days 4 and 14) and across all post-baseline time points.

Detailed methods for analyses of all safety variables will be provided in the SAP.

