## 6.1 Missing Data

Unless otherwise stated, missing data will be handled using the following approach:

- Analyses performed for the mITT population will use the method of last observation carried forward (LOCF) to impute missing values. No imputation for missing data will be performed for the safety population.
- For start date, partial dates will have first day of the month imputed if day is missing, and January of that year will be imputed if month is missing. If both day and month are missing, January 01 will be imputed.
- For end date, partial dates will have last day of the month imputed if day is missing, and December of that year will be imputed if month is missing. If both day and month are missing, December 31 will be imputed. An exception is that missing dates of prior and concomitant medications will not be imputed.
- Where severity or relationship is missing for adverse events, most conservative imputation will be made; in that a missing severity will be imputed as 'severe' and a missing relationship as 'related'.

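### SAP 10.1.1 drops the treatment-emergent limit that Protocol 9.3.2 places on the two serious-AE rows, and SAP 1.1 does not declare the change

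*SAP*

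**What the plan says.** Protocol section 9.3.2 sets out the adverse-event tables. After the rows for all TEAEs and treatment-related TEAEs, the list continues with "all serious TEAEs, treatment-related serious TEAEs, and all adverse events leading to premature discontinuation of study treatment". The synopsis plans the same rows.

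SAP section 10.1.1 gives the same list in the same order for Part 2, "tabulated by PT using counts and percentages by treatment groups". It keeps the treatment-emergent limit for the first two rows. For the next rows it reads "all serious AEs, treatment-related serious AEs, and all adverse events leading to premature discontinuation of study treatment". The discontinuation row matches the protocol; the two serious rows do not.

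SAP section 1.1 lists the changes from the protocol: the per-protocol analysis, the ANOVA by baseline IOP stratum, and the descriptive statistics by stratum. The serious-AE rows are not among them.

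Protocol sections 8.7 and 8.7.1 collect adverse events from consent to study exit. A condition found before dosing that is not judged to predate consent is handled as follows: "Otherwise, the condition should be reported as a pre-treatment adverse event".

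On missing values, SAP section 6.1 says: "Where severity or relationship is missing for adverse events, most conservative imputation will be made". A missing relationship becomes related. SAP section 10.1.1 repeats the rule. Neither place excepts events that start before the first dose.

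**The concern.** The two documents specify different tables. A programmer working from the SAP would apply the treatment-emergent flag to the first two rows, because the SAP names it there, and would leave it off the two serious rows. Serious events between consent and first dose would then be counted under the arm to which the subject was later assigned, although no study drug had been given when they began.

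Safety is a main objective of the study, and the Part 2 arms are small, so a single subject visibly moves a percentage in a row that readers look at first. Because the change is undeclared, a reader holding the protocol would take the row to contain treatment-emergent events only.

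**Working it through.** The plan states no figure to reproduce. The check compares the texts, traces one event through both sets of rules, and works out the weight of one subject.

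**Inputs**
- Serious rows: Protocol 9.3.2 and synopsis; SAP 10.1.1.
- Treatment-emergent definition, SAP 10.1.1: onset in the treatment period, or a pre-existing condition that worsens after the first dose.
- Collection window, Protocol 8.7: consent to exit.
- Population for safety tables, SAP 4 and 5.4: treated subjects.
- Arm sizes, SAP 3: about 24 per AGN-227535 group and 12 on timolol.
- Imputation rule: SAP 6.1 and 10.1.1.

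**Tracing one event.** Take a serious event that starts during washout and does not worsen after the first dose, in a subject who still qualifies and is dosed. By the SAP's own definition it is not treatment-emergent. The table shows how many subjects it adds to each row.

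| Row | Protocol 9.3.2 | SAP 10.1.1 as written |
|---|---|---|
| Serious events | 0 | 1 |
| Treatment-related serious events, relationship recorded as not related | 0 | 0 |
| Treatment-related serious events, relationship missing | 0 | 1 |

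The first line needs no missing data. The third line needs a blank relationship that survives to database lock. If the event worsens after the first dose it is treatment-emergent, and both documents count it in the serious row.

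**Weight of one subject**, 100/n:
- AGN-227535 arm: 100/24 = 4.17, about 4.2%.
- Timolol arm: 100/12 = 8.33, about 8.3%.

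**After the fix.** With both serious rows limited to treatment-emergent events, this event adds 0 to each row whether or not its relationship is missing. The imputation rule can therefore stay as it is for these rows.

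**The case against.** The case on the other side is that this is a terminology slip with little consequence.

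- The SAP says it is to be read together with the protocol, which gives the treatment-emergent wording in two places. The authors may simply have meant the serious rows as subsets of the TEAE rows.
- SAP 10.1.1 also plans an SAE listing and a TEAE listing. A pre-dose serious event that does not worsen would appear in the first and not in the second, so a careful reader could find it.
- A row of all serious events is over-inclusive and hides no harm.
- The tables cover Part 2 only; Part 1 has no adverse-event summary. They do not drive decisions: dose selection rests on Part 1 data (Protocol 3.4), and safety data are reviewed by the sponsor on an ongoing basis (Protocol 3.3.1).
- Few subjects would be affected. Eligibility is confirmed again on Day 1 before dosing, and those who fail leave as screen failures (Protocol 8.3.1), outside the Safety population.

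All of this stands as a reason to rate the point as minor. None of it reconciles the two texts: a listing does not correct a percentage in a table, and the SAP does not say that the serious rows are subsets of the TEAEs.

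Two stronger readings are tempting, and the documents support neither.

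- A reader might infer that washout events will commonly be reported as drug-related SAEs, on the view that relationship is left blank before any drug is given. No section says this. Protocol 8.7.3 calls for a relationship determination, the SAE form in 8.7.4 asks for a statement on relatedness, the source notes in 10.4.1 include it, and queries are to be resolved before lock (Protocol 9, SAP 6). The route exists in the wording but should rarely be taken.
- A reader might compare the pre-dose period of up to 50 days with the 14 treatment days and conclude that a large share of counted SAEs would precede dosing. That treats a share of calendar time as a share of events. It needs a constant event rate and ignores the removal of ineligible subjects on Day 1.

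**Conclusion.** The inconsistency is certain on the text, and its practical effect is minor. As written, the SAP counts a pre-dose serious event in a later-dosed Part 2 subject in that arm's serious row, where the protocol would not. The effect per affected subject is 4.2 percentage points in an AGN-227535 arm or 8.3 in the timolol arm, taking the planned sizes of 24 and 12. Entry into the treatment-related serious row is a secondary and unlikely consequence that depends on a missing relationship.

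This rests on three assumptions: the tables are programmed to the SAP's literal wording, the subject is dosed after the event, and the event does not worsen after the first dose. The documents give no basis for estimating how many such events to expect, so no expected count is offered.

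**What to change.** In the Part 2 table list of SAP 10.1.1, replace "all serious AEs, treatment-related serious AEs, and all adverse events leading to premature discontinuation of study treatment" with the wording of Protocol 9.3.2: "all serious TEAEs, treatment-related serious TEAEs, and all adverse events leading to premature discontinuation of study treatment". If the wider serious rows are intended, declare and explain them in SAP 1.1 instead.

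No change to the imputation rule is needed for these rows, and no extra listing is needed because the planned SAE listing already shows pre-treatment serious events. The cost is one sentence of SAP wording and a treatment-emergent filter on two table rows, made before database lock. Data collection and trial conduct are unaffected.

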#### **10.1.2 Electrocardiogram (ECG)**

For Part 1 of the study, baseline ECG parameters (Heart rate, PR Interval, QRS Duration, QT Interval, and QTc Interval) along with interpretation whether the subject's ECG is normal or abnormal will be listed by cohort treatment groups.

For Part 2 of the study, ECG parameters from baseline and post-baseline visits will be listed by cohort treatment groups. Change from baseline will also be presented in the listing.

#### **10.1.3 Biomicroscopy**

Slit-lamp biomicroscopy will be listed for Part 1 and 2 of the study by cohort treatment groups. Parameters with positive (no zeros or missing) findings will be presented. At any timepoint, a parameter will be omitted if there is no positive finding on either eye. Potentially clinically significant findings will also be flagged on the following category:

- Hour-matched change from baseline is of  $\geq 2$  grade worsening

The biomicroscopy Case Report Form (CRF) includes multiple categories, each of which includes multiple parameters to be evaluated. If the CRF's leading question "Were there any biomicroscopic findings?

(Yes/No)" is answered "No", then all parameters in all categories are to be treated as zero score or negative grade, even though they will show as "missing" in the database. If the CRF's leading question is answered "Yes", then the leading question of each category "Were there any /category/ findings (Yes/No)?" must be answered. If the category's leading question is answered "No", then all parameters in the category are to be treated as zero score or negative grade, even though they will show as "missing" in the database. Thus, a parameter with a "missing" value in the database will be treated as either zero score or negative grade under either of the two conditions below:

1. When the CRF's leading question about any biomicroscopic findings is answered "No".
2. When the CRF's leading question about any biomicroscopic findings is answered "Yes" and the category's leading question about any findings is answered "No".

#### **10.1.4 Vital Signs**

For Part 1 and 2 of the study, vital signs will be listed by cohort treatment groups, visit, hour and measurement position (supine or standing). Change from baseline and change from supine to standing will be presented in the listing.

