### Medical Conditions

1. Uncontrolled systemic disease.
2. History of orthostatic hypotension.
3. Female who is pregnant, nursing, or planning a pregnancy, or female of childbearing potential not using a reliable means of contraception (see Section 6.4).
4. Abnormal anatomy of nasolacrimal drainage system (eg, nasolacrimal duct obstruction).
5. History of chronic alcohol consumption or drug addiction.
6. Contraindications to topical beta-blocker therapy including bronchial asthma; a history of bronchial asthma; chronic obstructive pulmonary disease; second- or third-degree atrioventricular block; overt cardiac failure; cardiogenic shock.
7. History of or current diagnosis of cardiac arrhythmia.
8. Heart rate < 55 beats per minute while in a resting supine position.
9. Blood pressure decrease from the supine measurements of at least 20 mm Hg (systolic) or of at least 10 mm Hg (diastolic) after 3 minutes of standing.
10. Systolic blood pressure < 90 mm Hg while in a resting supine position.

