**Part 2 - Days 4 and 14/Exit (Hour 2) ( $\pm 10$  minutes)**

- Postural (supine/standing) blood pressure and heart rate
- ECG (Day 14/Exit only)
- Macroscopic (gross) hyperemia evaluation

- Slit-lamp biomicroscopy
- IOP (GAT)
- Visual Field (may occur at any time from Hour 2 prior to pupil dilation) (Day 14/Exit only)

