### **9.3. Methods of Analyses**

In general, data will be summarized with descriptive statistics which will include sample size, mean, standard deviation, median, minimum and maximum for continuous variables and frequency and percentage for categorical variables.

Part 1: All safety and IOP-lowering effects tabulations will provide descriptive statistics by cohort.

Part 2: For continuous variables, treatment groups will be compared using analysis of variance covariance techniques or two-sample t-tests. Nominal variables will be analyzed using Pearson's chi-square test or Fisher's exact test.

Analyses performed for the mITT population will use the method of last observation carried forward (LOCF) to impute missing values. No imputation for missing data will be performed for the PP or safety populations.

As this is an exploratory trial, all treatment comparisons will be made at the two-sided  $\alpha = 0.05$  level without adjustment for multiple comparisons.

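### Part 2 blood pressure and heart rate are only listed, so post-dose crossings of the protocol's own entry limits that are not recorded as adverse events are neither flagged nor counted by arm.

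*SAP*

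**What the plan says.** **How vital signs are reported.** SAP 10 sets the general rule: "Listings will be presented for all of the safety parameters (section 5.4) for Part 1 and 2 of the study", with AEs as the exception. SAP 10.1.4 applies it to vital signs, listed by group, visit, hour and position, and adds two derived columns: "Change from baseline and change from supine to standing will be presented in the listing". It gives no threshold, mean or count.

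**What is flagged or summarised.** Only two kinds of measurement get a flag: "For slit-lamp biomicroscope and visual acuity parameters, potentially clinically significant findings will be flagged according to pre-defined criteria in the listings". SAP 6.2 confines descriptive statistics to demographics and baseline data, Part 2 IOP and Part 2 AEs.

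**What the protocol says.** Protocol 9.3 states: "In general, data will be summarized with descriptive statistics". Protocol 9.3.2 leaves detailed safety methods to the SAP. SAP 1.1, which lists changes from the protocol, does not mention vital signs.

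**The limits.** Protocol 4.2 gives numeric limits in three exclusion criteria: supine heart rate below 55 (criterion 8), a postural fall (criterion 9, "Blood pressure decrease from the supine measurements of at least 20 mm Hg (systolic) or of at least 10 mm Hg (diastolic"), assessed after 3 minutes of standing) and supine systolic pressure below 90 (criterion 10).

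**The measurements.** Table 3 and protocol 8.4.2 schedule supine and standing blood pressure and heart rate at Hours 0 and 2 on Days 1, 4 and 14.

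**The concern.** Part 2 measures the same quantities that the entry criteria limit, in the same two positions, before and after dosing and alongside an active control. The SAP then does not carry them beyond a listing. A subject whose pressure falls on standing at Hour 2 without symptoms appears as an unmarked row, and no output shows how many such subjects each arm had.

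This is a first-in-human study. Acceptable safety is a stated hypothesis for both parts, and SAP 5.4 names vital signs among the safety assessments. Timolol has cardiac contraindications of its own (exclusion 6), so crossings on AGN-227535 are hard to interpret without the matching count on timolol. At stake is the completeness of the safety description. No efficacy conclusion depends on it.

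**Working it through.** The documents state no figure for vital signs, so there is nothing to reproduce. The power figures in protocol 9.2 and SAP 3.1 concern IOP.

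**1. Is there another route to a count by arm?**
- SAP 10.1.1 tabulates Part 2 AEs by preferred term and treatment group. This captures a crossing only if it is recorded as an AE.
- Protocol 12.2.1.7 sends clinically relevant laboratory changes to the AE form. No visible text does the same for blood pressure or heart rate.
- The scheduled AE query is at Hour 0 (Table 3, protocol 8.4.2), before the Hour 2 reading. On Day 14 no scheduled query follows that reading, although protocol 8.7 requires AEs to be reported throughout.

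The AE table therefore covers recorded events, and asymptomatic or unrecorded crossings remain outside it.

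**2. How many readings are involved?** Inputs: 24 + 24 + 12 = 60 treated subjects if two doses are selected (protocol synopsis).

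| Sets after the first dose | Per subject | Pairs in 60 subjects |
|---|---|---|
| Hour 2, Days 1, 4 and 14 (after a same-visit dose) | 3 | 3 × 60 = 180 |
| Hour 0, Days 4 and 14 (before that morning's dose) | 2 | 2 × 60 = 120 |
| Total | 5 | 300 |

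The 180 Hour 2 pairs split as 72 + 72 + 36 across the arms. With one dose selected they would be 3 × 36 = 108. The limits do not use every value: standing heart rate has none, and standing pressures enter only as a fall from supine.

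**3. Is a baseline needed?** Table 1 footnote b makes Day -1 supine only. The three limits use absolute supine values or a within-visit difference, so they can be applied without a standing baseline.

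**4. What would a count show?** The documents give no crossing rate, so I assume true rates p of 5%, 10% and 20% of subjects. The chance of seeing at least one affected subject is 1 − (1 − p)^n.

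| Assumed p | n = 24 | n = 12 |
|---|---|---|
| 5% | 71% | 46% |
| 10% | 92% | 72% |
| 20% | 99.5% | 93% |

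Exact (Clopper-Pearson) 95% intervals:
- 0/24: upper bound 1 − 0.025^(1/24) = 14.2%
- 0/12: upper bound 1 − 0.025^(1/12) = 26.5%
- 4/24: 4.7% to 37.4%

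**5. Would a test help?** Exact power of Fisher's test, 24 versus 12, two-sided 0.05, with an assumed timolol rate of 5%, is 13% against 25%, 57% against 40% and 81% against 50%. A test would miss most plausible differences, so the output should be descriptive.

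**The case against.** **Listing-only is a consistent choice.** Protocol 9.3.2 delegates safety methods to the SAP, the trial is exploratory, and ECG, laboratory tests, hyperemia and comfort are treated the same way. The protocol's summary sentence is also qualified as general. This stands as far as it goes: the plan is not incoherent. It does not explain why the departure is missing from SAP 1.1, or why measurements with ready numeric limits get no flag when slit-lamp and acuity findings do.

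**The yield is coarse.** True: with arms of 24 and 12 the intervals are wide. That argues for a descriptive count without a test. It does not argue for no count.

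Three stronger readings are tempting, and the documents do not support them.

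- *A systemic effect could go unreported.* Every value is listed with the supine-to-standing change, recorded AEs are counted by arm, and protocol 3.3.1 has the sponsor review all available safety data on an ongoing basis. What is missing is marking and comparison.
- *The entry limits identify the drug's main hazard or act as on-treatment thresholds.* Protocol 4.5 gives no specific rationale for exclusions 1 to 10, the benefit/risk text is largely redacted, and the heart-rate limit may reflect beta-blocker precautions for the timolol arm. No visible text applies the limits after entry.
- *The ECG comparison breaks the hour-matching rule, so the baseline ECG should move.* The Part 2 baseline ECG is at Hour 0 and the Day 14 ECG at Hour 2, but SAP 6 provides a fallback when no hour-matched value exists. A time-of-day shift common to the arms affects within-arm change, not the comparison with concurrent timolol. The Day -1 ECG also supports eligibility (inclusion 3h), needs a cardiologist's confirmation before dosing (protocol 7.3), and could be moved only by protocol amendment.

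**Conclusion.** The point holds as a reporting gap. Part 2 blood pressure and heart rate have no flag and no summary by arm, and SAP 1.1 does not record this as a change from protocol 9.3. Crossings that are asymptomatic or not recorded as AEs are listed but never marked or compared between each AGN-227535 dose and timolol.

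Its size is 180 supine/standing pairs after a same-visit dose, plus 120 pre-dose pairs on later visits. This assumes that two doses are selected and that all 60 subjects are treated and measured as scheduled. How many crossings would be found is unknown; the detection chances rest on assumed rates of 5% to 20%.

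This is a cheap improvement that serves the stated safety hypothesis. It does not affect the IOP analyses.

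**What to change.** **In SAP 10 and 10.1.4:**
- Flag each Part 2 record after the first dose that meets any of the protocol's entry limits: supine heart rate below 55, supine systolic below 90, or a supine-to-standing fall of at least 20 mm Hg systolic or 10 mm Hg diastolic.
- Tabulate by arm the number and percent of subjects with any such value, overall and at Hour 2, with exact 95% confidence intervals and no formal test.
- State that these are reporting flags only and do not govern treatment.

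**In SAP 10.1.2**, at most, add a note that the Part 2 ECG change compares Day 14 Hour 2 with Day -1 Hour 0 and is best read against the concurrent timolol arm. Leave the baseline ECG where it is.

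**Cost:** one flag variable and one small table from data already scheduled for collection, with no new assessment. The drawback is imprecision, so a zero count must not be read as evidence of no effect.
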